8.2. Other safety endpoints

No other safety endpoints are foreseen in this study.

9. Exploratory analysis

In the course of this study, exploratory analysis is not envisaged.

10. Interim analysis

Interim data analysis is not planned for this study.

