### **9.3.4 Documentation of adverse events**

Any AEs (non-serious and serious) observed after the subject has given informed consent to participate in a particular study and prior to the subject's last visit in the course of the study should be documented on the AE page in the case report form (CRF).

Information on AE should be collected by unobtrusive interviewing the subject on each visit during the study. AEs can also be identified if the subject reports them voluntarily during a visit, between visits, or during a physical examination, laboratory tests, or other examinations. An appropriate medical care should be provided in all AEs. The treatment may include one or more of the following: no action taken (i.e., follow-up only); dose adjustment / temporary discontinuation of IMP; complete discontinuation of IMP due to this AE; prescription of concomitant medicinal product; administration of non-drug therapy; hospitalization of the patient / extension of hospitalization. The treatment of AE shall be documented in CRF. Besides, actions taken with respect to IMP should be recorded and classified into one of the following categories: no change, discontinuation, dose reduction, dose increase, temporary discontinuation, unknown and not applicable. Concomitant medications, other treatment methods or changes in the IMP regimen should be clearly indicated and documented.

Medical conditions / diseases that occurred prior to the IMP administration are considered as AE only in the case of exacerbation after inclusion of the patient in the study. Deviations of laboratory parameters and results of other studies from the norm are considered AE (only if they entail the development of clinical signs or symptoms), clinically significant or require treatment.

After the detection of AE, the Investigator should continue the follow-up as indicated below. In all cases, AE outcomes should be documented and classified into one of the following categories: no resolution / unchanged, deterioration, recovery / resolution, improvement / in the process of recovery, recovery / resolution with consequences, fatal outcome or unknown. The AE assessment should be carried out at each scheduled visit (or more often, if necessary). The Investigator should

document in the CRF any changes in seriousness, severity, suspected association with IMP, AE related interventions, and outcome.

Adverse events, observed in the period between giving the consent and the last visit

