#### 10.1.4 Analysis of safety parameters

Safety parameters should be evaluated at each visit planned in this study, as well as at unscheduled visits.

Safety evaluation will be based on the following parameters (between Visits 1 and 3), compared between the investigational medicinal product and placebo:

Frequency of adverse events (AEs) and/or serious adverse events (SAEs) in the treatment groups, including:

1. Determination of the overall incidence in:
  - I. adverse events (AEs), regardless of their association to the treatment;
  - II. AEs related or possibly related to the medicinal product administration;
  - III. AEs requiring therapy discontinuation.

AEs recording will be based on spontaneous report by the patient, as well as on the results of a patient survey by a physician.

Adverse events will be encoded according to the last update of MedDRA terminology. They will be represented by a preferred term (PT) and a system organ class (SOC).

2. AEs incidence according to the results of the vital signs evaluation (HR, BP, BT, RR) at each visit vs placebo

Changes in the main vital signs over time and the frequency of pathological abnormalities revealed during physical examination will be summarized in groups, and a comparison will be made between groups using appropriate tests for quantitative and qualitative data (see below). Quantitative data will be compared using the t-test or the Mann-Whitney test, depending on the normality of the distribution (which will be evaluated using the Shapiro-Wilk test). Qualitative data will be compared using the Fisher's exact test or the chi-square test, depending on the number of prospective observations in one cell (<5 or ≥5).

3. AEs incidence according to the results of laboratory examinations on Days 7(± 2) and 15(± 2) and AEs incidence according to the ECG results 15(± 2) vs placebo;

Variations in the results of laboratory tests (carried out in the central laboratory) over time and the rate of pathological deviations from the norm of the study results (based on the central laboratory reference values), as well as the deviations rate of the ECG results at the Visit 3 will be summarized by groups, and comparison between groups shall be made using appropriate tests for quantitative and qualitative data (see paragraph 2).

4. AEs incidence according to the everyday patients' diaries records of well-being self-evaluation.

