Patient complaints based on the results of the daily records of well-being self-assessment in the diary will be summarized into groups, and comparison between groups shall be made using appropriate tests for quantitative and qualitative data. Gastrointestinal AEs (determined using standardized MedDRA requests for the corresponding symptoms), regarded by the Investigator as associated with the study therapy, will be analyzed separately. Descriptive statistics methods will be used for the results. Comparison of the incidence of new AEs in the study groups will be carried out using the Fisher's exact test or the chi-square criterion, depending on the number of prospective observations in one cell ( $<5$  or  $\geq 5$ ); the comparison of severity degree (and possible causal relationship between received medicinal product and AE) will be carried out using the Cochran – Armitage test for linear trends for ordered categorical data.

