- A number of days of using symptomatic therapy to relieve symptoms of acute diarrhea in the treatment group as compared to the placebo group.

Due to the obvious difference between the distribution of these indicators from the normal (they have a discrete distribution), the nonparametric Mann–Whitney–Wilcoxon test implemented in the `wilcox.test` function will be used for intergroup comparison.

3. Other secondary endpoints:

- Weight change at Visit 3 compared with Visit 1 in the placebo group as compared to the treatment group. This BKT can have a distribution close to normal. Accordingly, at the first stage, the normality of the distribution will be assessed (using the Shapiro–Wilk test implemented in the shapiro.test function), at the second stage, either the t-test (t.test function) or the Mann–Whitney–Wilcoxon test (wilcox.test function) will be used.
- Stool consistency change (according to Bristol Stool Scale) (according to the diary) in the treatment group as compared to the placebo group; any individual changes in stool consistency will be classified as improved/unchanged/worsened, and the difference between the groups will be analyzed using chi-square criterion (chisq.test function).

8. Safety analysis

Safety parameters will be evaluated at every planned or unscheduled visit.

The safety assessment will be based on the following indicators (between Visits 1 and 3) compared between the investigational medicinal product and placebo:

- Changes in the vital signs over time and the incidence of pathological abnormalities revealed during the physical examination will be summarized by the group; a comparison will be made between the groups using appropriate tests for quantitative and qualitative data.

The data will be checked for compliance with the normal distribution law using the Shapiro–Wilk test.

Intergroup comparison of secondary endpoints related to quantitative scales will be performed using Student's t-test for independent samples if the data correspond to the normal distribution law; otherwise, the Mann–Whitney U test will be applied to independent samples.

Intergroup comparisons of secondary endpoints related to categorical scales will be performed using Pearson's chi-square test if the number of points in each cell of the crosstab is ≥ 5 , or Fisher's exact test if at least one of the crosstab cells contains < 5 points.

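### The SAP's safety section leaves out protocol-specified comparisons of laboratory values, laboratory and ECG abnormality rates and three AE summaries, then closes the list

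*SAP*

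**What the plan says.** Protocol 10.1.4 sets out four groups of safety analyses.

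- Item 1 asks for the overall incidence of all AEs, of "AEs related or possibly related to the medicinal product administration" (II) and of "AEs requiring therapy discontinuation" (III).
- Item 2 covers vital signs and physical examination.
- Item 3 covers "Variations in the results of laboratory tests (carried out in the central laboratory) over time and the rate of pathological deviations from the norm", "as well as the deviations rate of the ECG results at the Visit 3 will be summarized by groups", and a comparison between groups. It uses the tests named in item 2: t-test or Mann-Whitney for quantitative data, Fisher or chi-square for qualitative data.
- Item 4 covers diary-based events and adds: "Gastrointestinal AEs (determined using standardized MedDRA requests for the corresponding symptoms), regarded by the Investigator as associated with the study therapy, will be analyzed separately".

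SAP 8 has a single indicator of its own: "Changes in the vital signs over time and the incidence of pathological abnormalities revealed during the physical examination will be summarized by the group". SAP 8.1 then lists AE incidence overall and by source (physical examination, vital signs, ECG, laboratory, diary), each against placebo. It plans Fisher or chi-square tests for incidence and Cochran–Armitage tests for severity and causality. SAP 8.2 reads: "No other safety endpoints are foreseen in this study".

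Three other places matter. Protocol 10.1 describes its own statistical text as brief and leaves the complete analysis to the SAP. Protocol 9.3.4 sets the AE threshold for test results, beginning "Deviations of laboratory parameters and results of other studies from the norm are considered AE (only if they entail" and going on to name clinical signs or symptoms, clinical significance and need for treatment. Protocol 10.7 requires departures from the original statistical plan to be described and justified.

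**The concern.** Safety is the trial's stated secondary objective (protocol 4.2), and the SAP introduction says that the results are meant to support registration. The SAP is the document that will be programmed. Where it is narrower than the protocol and says that nothing else is foreseen, the omitted analyses will either not be run or be added late and look post hoc.

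The laboratory and ECG comparisons in item 3 can show a modest shift in group means or in abnormality rates that no single investigator would report as an AE. If they are omitted, such a shift in ALT, AST, bilirubin, white cells or ECG findings has no planned route into the report. The GI item also matters because protocol 3.1.1 names mild gastrointestinal disorders as the reported adverse reactions to the product.

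**Working it through.** **Base for the counts.** The plan's sample size reproduces from the printed formula: (1.960 + 0.842)² × [0.26 × 0.74 + 0.15 × 0.85] / 0.11² = 207.5, rounded up to 208 per group. That gives 416 in total, and 416 / (1 − 0.20) = 520 randomized. The point does not depend on this calculation; 520 is used only as the maximum number of patients.

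**Item-by-item comparison.**

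| Protocol 10.1.4 | SAP 8 to 8.2 | Status |
|---|---|---|
| 1.I all AEs | AE incidence, Fisher or chi-square (8.1) | Kept |
| 1.II incidence of related AEs | Causality trend test (8.1); no explicit patient-level incidence | Partly kept |
| 1.III incidence of AEs requiring discontinuation | Action taken with the product described per AE (8.1); no comparison stated | Partly kept |
| 2 vital signs, physical findings | Compared between groups (8) | Kept |
| 3 laboratory values over time | None | Omitted |
| 3 laboratory abnormality rate | Only abnormalities that become AEs (8.1) | Omitted below the AE threshold |
| 3 ECG deviation rate, Visit 3 | Only deviations that become AEs (8.1) | Omitted below the AE threshold |
| 4 related GI AEs by standardized MedDRA queries | None; diary GI symptoms are an efficacy endpoint (7.2) | Omitted |

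**Data affected.** The visit schedule (protocol 5.2.3.1, Table 6) takes a blood count and chemistry at Visits 1, 2 and 3, and an ECG at Visits 1 and 3. SAP 5 compares all pre-treatment laboratory and instrumental data between groups, so Visit 1 is covered. What remains is:

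- blood samples: 520 × 2 = 1,040 at most;
- scheduled ECGs: 520 × 1 = 520 at most.

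If the whole planned 20% withdrawal fell before Visit 2 (an assumption), the figures would be 416 × 2 = 832 and 416. The SAP therefore compares laboratory values before a treatment effect is possible and not afterwards.

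**Denominators.** The AE layouts in SAP Appendix 1 (Tables 5 and 6) express counts as a percentage of AEs, not of patients. If one arm had twice as many related and twice as many unrelated AEs as the other, the related share would be the same in both. The causality comparison therefore does not replace the incidence of related AEs. Protocol 10.1.4 says overall incidence, and the Synopsis speaks of analysing subjects with AEs, so incidence is read here as patient-level.

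**Reference ranges.** Item 3 assumes a central laboratory and its reference values. Protocol 5.2.3.2.3 says that the blood count and chemistry are done in the study site's laboratory, and the Synopsis allows up to 40 sites. The restored abnormality rate cannot be programmed until this is settled.

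**The case against.** The strongest reply is that the SAP keeps the safety parameters as the protocol itself defines them. Protocol 5.1.2, 9.1 and 9.2 all express laboratory and ECG safety as AE incidence against placebo, and SAP 8.1 repeats that. This stands. A reader might infer from SAP 8.2 that laboratory and ECG safety has been dropped altogether; the documents do not support that. An abnormality judged clinically significant, or needing treatment, counts as an AE without symptoms, so what is lost is the sub-threshold part of a short panel.

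The reply on causality also has force. Protocol 9.3.3 allows only two categories, suspected and not suspected, and with two categories the Cochran–Armitage test is essentially the 2×2 chi-square. A between-arm test on relatedness therefore exists. It works on AEs, however, and leaves the patient-level incidence unstated.

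A reader might also infer that AEs leading to discontinuation will not be tabulated by arm. That goes too far. Discontinuation is a recorded category of action taken (protocol 9.3.4), SAP 8.1 describes action taken, and the generic Table 6 layout could show it by group with a Fisher p-value. Other Appendix 1 layouts could likewise carry laboratory values. But no SAP text assigns any of these variables to a table, so the analysis is possible rather than planned.

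Finally, the diary GI symptoms in SAP 7.2 are compared between arms, but irrespective of causality and as efficacy. They do not replace item 4.

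**Conclusion.** The gap is real but limited. Between protocol 10.1.4 and SAP 8 to 8.2, the planned comparisons of laboratory values, of laboratory and ECG abnormality rates as such, and of query-based related GI AEs disappear. The patient-level incidence of related AEs and of AEs requiring discontinuation is no longer explicit. No justification is given, and the 8.2 sentence makes it hard to treat the omissions as oversights that programmers would fill. At most 1,040 post-baseline blood samples and 520 Visit 3 ECGs are affected, and only for changes below the AE threshold.

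Two broader conclusions do not follow. It would be wrong to say that most objective safety data escape a between-arm comparison, because vital signs, physical findings and laboratory- and ECG-derived AEs are all compared. Nor do the omissions by themselves prove a breach of protocol 10.7. That section allows a departure to be justified by protocol amendment or in the final report, and requires the list in the SAP only in the latter case.

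The conclusion rests on reading 9.3.4 as three alternative conditions despite its misplaced parenthesis, and on taking the SAP as written. The primary endpoint and sample size are not affected. The point deserves correction before unblinding.

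**What to change.** Delete or qualify the sentence in SAP 8.2, and restore protocol 10.1.4 items 1.II, 1.III, 3 and 4 in SAP 8:

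- laboratory parameters at Visits 2 and 3 by arm, with t-test or Mann-Whitney;
- laboratory abnormality rates at Visits 2 and 3 and the ECG deviation rate at Visit 3 by arm, with Fisher or chi-square;
- the number and percentage of safety-population patients with a related AE, with an AE requiring discontinuation, and with a related GI AE selected by standardized MedDRA queries, each with Fisher or chi-square.

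Assign each output to a table layout, with patients as the denominator. If any of these analyses is meant to be dropped, document and justify that by the route in protocol 10.7. Reconcile protocol 10.1.4 with 5.2.3.2.3 on which laboratory's reference ranges define an abnormality.

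Effect estimates with 95% confidence intervals would help the reader but go beyond 10.1.4 and are optional. The cost is SAP text and a few table shells. The data are already collected, and neither the visits nor the sample size change.

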Appendix 1. Table layouts

Table No. 1. Example of a statistical table for a quantitative variable

Visit	Group	Parameter	Variable name
Visit number	Group 1	N	
		Missed	
		Mean	
		95% CI	
		SD	
		Median	
		Min	
		Max	
		Q1	
		Q3	
	IQR		
	Group 2	N	
		Missed	

STATISTICAL ANALYSIS PLAN

Visit	Group	Parameter	Variable name
		Mean	
		95% CI	
		SD	
		Median	
		Min	
		Max	
		Q1	
		Q3	
		IQR	

Table No. 2. Example of a group comparison table for a quantitative variable

Visit	No.	No.	No.	No.
Variable	variable name			

STATISTICAL ANALYSIS PLAN

Shapiro–Wilk test, p-value	Group 1				
	Group 2				
Student's t-test, p-value					
Mann–Whitney test, p-value					

Table No. 3. Example of a repeated comparison table for a quantitative variable

Variable	Group	Visit	Friedman test/ ANOVA for repeated measurements	Wilcoxon test/ Student's t-test for repeated measurements
variable name	Group 1	Comparison of visits		
		No. vs. No.		

STATISTICAL ANALYSIS PLAN

Variable	Group	Visit	Friedman test/ ANOVA for repeated measurements	Wilcoxon test/ Student's t-test for repeated measurements
		No. vs. No.		
		No. vs. No.		
		No. vs. No.		
		No. vs. No.		
		No. vs. No.		
	Group 2	Comparison of visits		
		No. vs. No.		
		No. vs. No.		
		No. vs. No.		
		No. vs. No.		

STATISTICAL ANALYSIS PLAN

Variable	Group	Visit	Friedman test/ ANOVA for repeated measurements	Wilcoxon test/ Student's t-test for repeated measurements
		No. vs. No.		
		No. vs. No.		

Table No. 4. Example of a statistical table for a categorical variable

Variable	Visit	Group	Variable value	Amount	% by group	% by groups for visit	Fisher's test, p-value
variable name	No.	Group 1	value				
			value				
		Group 2	value				
			value				

STATISTICAL ANALYSIS PLAN

Table No. 5. Example of a table of adverse events for calculating the number of all adverse events

Adverse events	Group	Amount	% of the number of AEs in the group	% of the total number of AEs	Binomial test, p-value
All adverse events	Group 1				
	Group 2				
SOC	Group 1				
	Group 2				
PT	Group 1				
	Group 2				

Table No. 6. Example of a table of adverse events for calculating the number of adverse events in the context

Adverse events	Group	variable name	Amount	% of the number of AEs in the group	% of the total number of AEs	Fisher's test, p-value
	Group 1	value				
		value				

STATISTICAL ANALYSIS PLAN

Adverse events	Group	Variable name	Amount	% of the number of AEs in the group	% of the total number of AEs	Fisher's test, p-value
All adverse events	Group 2	value				
		value				
		value				
		value				
SOC	Group 1	value				
		value				
		value				
	Group 2	value				
		value				
		value				
PT	Group 1	value				
		value				
		value				
	Group 2	value				
		value				

/Logotype: Research/

STATISTICAL ANALYSIS PLAN

Adverse events	Group	variable name	Amount	% of the number of AEs in the group	% of the total number of AEs	Fisher's test, p-value
		value

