8.1. Adverse events

Safety assessment will also be based on the following parameters (between Visits 1 and 3) compared between the investigational medicinal product and placebo:

Incidence of adverse events (AEs) and/or serious adverse events (SAEs) in the treatment groups including:

- Overall AE rate as compared to placebo;
- AE rate according to the results of physical examinations during each visit compared with placebo;
- AE incidence according to the assessment of the vital signs (HR, BP, BT, RR) at each visit as compared to placebo;
- AE incidence according to the ECG results on Day 15 (± 2) in comparison with placebo;
- AE incidence according to the results of laboratory examinations on Days 7 (± 2) and 15 (± 2) as compared to placebo;
- AE incidence according to the results of daily self-examination of the state of health recorded in Self-Observation Diary.

The study doctor will review the entries in the Self-Observation Diary. If the study doctor believes that the information in the Diary complies with the AE criteria, they will ask the patient about this event and document all information about the AE (including the causality assessment).

The AEs will be described according to the scheme given below:

- AE description
- Severity of the adverse event (meeting the severity criteria)
- AE severity
- AE duration
- Relation to the IMP
- Measures taken in relation to the investigational medicinal product
- Measures taken in relation to the patient

- **Outcome**

Adverse events will be coded according to the MedDRA

Methods of descriptive statistics will be used to represent the results. A comparison of the incidence of new AE cases in the study groups will be performed using the Fisher's exact test or the chi-square test, depending on the number of proposed observations in one cell (< 5 or ≥ 5), and a comparison of the severity (and the possible causality between the administered medicinal product and AE) will be conducted using the Cochran–Armitage test for linear trends for ordered categorical data.

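### SAP example Table 5 tests adverse-event counts with a binomial test that conflicts with the AE methods text, and no AE-specific shell shows the share of patients with an AE

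*SAP*

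**What the plan says.** SAP Appendix 1 has two layouts specific to adverse events.

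- **Table 5** counts AEs by group, with rows for all AEs, SOC and PT. Its percentages are per cent "of the number of AEs in the group" and per cent "of the total number of AEs". Its last column is "Binomial test, p-value", with no null proportion stated.
- **Table 6** is titled "Example of a table of adverse events for calculating the number of adverse events in the context". It splits the AEs by a further, unnamed variable, uses the same two denominators, and ends in a Fisher p-value.

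The methods text reads differently. SAP 8.1 lists "Overall AE rate as compared to placebo" among the safety parameters and then says: "A comparison of the incidence of new AE cases in the study groups will be performed", by Fisher's exact or chi-square test. Severity and causality go to Cochran–Armitage. Protocol 10.1.4 matches it: "Comparison of the incidence of new AEs in the study groups will be carried out" with the same tests. It also lists the overall categories to report: any AE, related AEs, and "AEs requiring therapy discontinuation".

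The protocol synopsis (Statistical Analysis) assigns chi-square or Fisher to study subjects with an AE or SAE, and Poisson regression to AE frequency. Neither SAP 8.1 nor Protocol 10.1.4 mentions Poisson regression. SAP 4.2.1 defines a safety population, so a patient denominator exists.

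**The concern.** Evaluating safety is the trial's stated secondary objective, and Protocol 10.1 calls its own section brief and leaves the complete analysis to the SAP. A programmer following the SAP meets one test in 8.1 and another in Table 5 and cannot satisfy both.

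If Table 5 is built as drawn, two things go wrong. The p-value treats every event as an independent observation, so a few patients with many AEs can create a difference between arms, and a difference in the number of patients affected can disappear. The first figure a safety reader looks for, the percentage of patients with at least one AE, is also absent from both AE shells.

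**Working it through.** **1. Unit and test, side by side**

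| Place | What is compared | Test |
|---|---|---|
| Protocol synopsis | subjects with an AE or SAE | chi-square or Fisher |
| Protocol synopsis | AE or SAE frequency | Poisson regression |
| Protocol 10.1.4 | incidence of new AEs, unit not stated | Fisher or chi-square; Cochran–Armitage for severity and causality |
| SAP 8.1 | as Protocol 10.1.4, unit not stated | as Protocol 10.1.4 |
| SAP Appendix 1, Table 5 | events | binomial, null not stated |
| SAP Appendix 1, Table 6 | events, by a further variable | Fisher |

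The only other use of the word binomial is the model family of the primary logistic regression (SAP 7.1), which is a different thing.

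**2. What the percentages can show**

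Let E1 and E2 be the AE totals of the two arms. In the row for all AEs, the first percentage is 100·E1/E1 = 100% in one arm and 100·E2/E2 = 100% in the other, whatever the data. The second is 100·E1/(E1+E2), the split of events between arms. Neither contains the number of patients treated or affected, so incidence per patient cannot be recovered.

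**3. Arm size for the illustrations**

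The documents give no AE figure to reproduce, so the planned arm size is used. The plan's formula with 0.26 v 0.15, two-sided 0.05 and 80% power gives (1.960+0.842)² × (0.1275+0.1924)/0.11² = 207.5, rounded up to 208. Then 208/0.8 = 260 randomized per arm, as stated.

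**4. Two worked cases at 260 per arm, with the binomial null assumed to be 0.5**

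- *Case A.* 40 v 20 events, 20/260 patients affected in each arm. Binomial: 2·P(X≥40), X~Bin(60, 0.5), p=0.013. Fisher on patients: p=1.0. The two tests answer different questions, so a count model is a useful third view. Plain Poisson regression gives p=0.011. With robust standard errors it gives p=0.023 if the 40 events are two per patient, and p=0.23 if one patient has 21 of them and 19 patients have one each.
- *Case B.* 40 v 40 events, 40/260 v 20/260 patients affected (15.4% v 7.7%). Binomial p=1.0. Fisher on patients p=0.009. Table 5 would show 100% and 50% in both arms.

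**5. False-positive rate with no true difference**

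Assumed: mean 0.5 AE per patient, 260 per arm, nominal two-sided 5%, Poisson or negative binomial counts. There were 40,000 simulations for the binomial test and 20,000 for the others.

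| Variance/mean of AEs per patient | 1 | 1.5 | 2 |
|---|---|---|---|
| Binomial on events | 4.4% | 9.9% | 15.0% |
| Plain Poisson regression | 4.7% | 10.9% | 16.0% |
| Poisson, robust errors | 4.8% | 5.1% | 4.9% |
| Fisher on patients | 4.1% | 4.0% | 3.9% |

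If no patient has more than one AE, the binomial test is conservative instead: 2.9%, 2.2% and 1.5% at incidences of 10%, 20% and 30%.

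**The case against.** The strongest reply is that these layouts are all labelled examples, while the operative text in SAP 8.1 and Protocol 10.1.4 already names an acceptable test and the synopsis already names subjects. Protocol 10.7 asks for deviations from the protocol's statistical plan to be listed and justified, and the SAP lists none. On that view the shell is mislabelled and no analysis has been replaced. This stands, and it limits the point to a conflict between shell and text. It does not remove the point, because these are the only AE layouts in the SAP.

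Second, patient-level information is not wholly absent. SAP 7.2 plans 2×2 tables of patients, with Fisher or chi-square, for gastrointestinal symptoms, any diarrhea and hospitalization as efficacy endpoints. These overlap with the product's known mild reactions. The generic Table 4 could also hold an AE yes/no variable. Both observations are correct, but SAP 7.2 does not cover overall AEs, SAEs or SOC/PT, and nothing assigns AEs to Table 4.

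Third, with equal arms a binomial test against 0.5 is the conditional comparison of two Poisson counts, so an event-level test is not foreign to a plan whose synopsis names Poisson regression. The simulation agrees: the two behave almost alike. This argues for correcting the Poisson standard errors too. It does not justify the binomial column.

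Fourth, the magnitudes rest on assumed inputs, and 21 AEs in one patient within 17 days is extreme. That is accepted. Repeat AEs are nonetheless realistic: the protocol's summary of a study in elderly volunteers, at the same strain and dose, reports 47 AEs in 15 people, 1 to 7 each. That study was small and uncontrolled, so it shows only that repeats occur.

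**Conclusion.** The concern holds as a conflict within the SAP and between the SAP and protocol. Table 5 attaches to event counts a test that no methods text names, with denominators that cannot show how many patients had an AE. That part needs no assumption. The statistical consequence does. With clustering at variance/mean 1.5 to 2, an assumed mean of 0.5 AE per patient and an assumed null of 0.5, the binomial test's false-positive rate is about 10% to 15%. Without clustering it is at or below nominal. The documents give neither AE rates nor overdispersion for this trial.

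Three stronger readings are tempting and not supported. A reader might infer that the SAP has dropped the patient-level AE comparison; SAP 8.1 retains Fisher or chi-square and no deviation is declared. A reader might infer that no patient-level tolerability data are planned; SAP 7.2 plans some. A reader might take 15% as this trial's error rate; it is an illustration. No success criterion rests on these tables, and the primary analysis and sample size are untouched. It should be corrected before the safety tables are programmed.

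**What to change.** - **Table 5:** show n (%) of safety-population patients with at least one AE, for overall, SAE, related, leading to discontinuation, and by SOC and PT. Compare arms by the Fisher or chi-square test already in SAP 8.1. Keep event counts as a descriptive column and delete the binomial p-value.
- **SAP 8.1:** state that AE incidence is counted in patients.
- **Table 6:** make it descriptive, or put its test on a patient basis in line with 8.1. That means Cochran–Armitage on each patient's worst severity or strongest causality, and Fisher or chi-square for other attributes.
- **Poisson regression of AE frequency:** say in the SAP whether it is kept. If kept, use robust or overdispersion-corrected standard errors, since the plain model shares the clustering problem. If dropped, list and justify the deviation under Protocol 10.7.

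The cost is one redrawn shell, one column removed or redefined, and a few sentences in the SAP. No new data are needed, because patient counts come from the same database. The Poisson item touches protocol text. If it is settled by amending the protocol instead of by a listed deviation, Protocol 11.2 treats changes that can affect statistical methods as substantial, and approval would be needed.
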